 - Liver function tests: total bilirubin ≤ 1.5 upper limit of normal (ULN; unless evidence of Gilbert's disease confirmed by uridine diphosphate-glucuronyltransferase [UGT] polymorphism); aspartate transaminase (AST) and alanine transaminase (ALT) ≤ 3 ULN; AST and ALT ≤ 5 ULN in case of liver metastases
 11. For women with childbearing potential, a negative pregnancy test within 7 days prior to initiation of the study drug
 12. Willingness to use an effective contraceptive method during the study and up to six months after the last dose is administered. Effective methods include the following: non-hormonal intrauterine device, barrier method (condoms, diaphragm) also in conjugation with spermicidal jelly, or total abstinence. Oral, injectable, or implant hormonal contraceptives are discouraged
 13. Written consent on an Institutional Review Board (IRB)/Independent Ethics Committee(IEC)-approved ICF prior to any study-specific evaluation

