6.4 Patients or Partners of Patients of Reproductive Potential

Pregnancy is an exclusion criterion and women of childbearing potential must not be considering getting pregnant, or become pregnant, during the study. Female patients who are more than 2 years postmenopausal or have had a hysterectomy will not be considered of childbearing potential. Female patients of childbearing potential must have a negative serum pregnancy less than 7 days prior to administration of the first dose lucitanib. If the serum pregnancy results are not available prior to dosing, a urine pregnancy test can be performed to confirm that the patient is not pregnant prior to dosing. Both values should be entered in the electronic case report form (eCRF). Another serum pregnancy test will be performed at the end-of-study visit.

Patients of reproductive potential (males and females) must practice an effective method of contraception during treatment and for 6 months following the last dose of lucitanib. Adequate contraception is defined as double-barrier method (i.e., condom plus spermicide in combination with a diaphragm, cervical/vault cap, or intrauterine device). Oral, injectable, or implant hormonal contraceptives are discouraged.

Patients will be instructed to notify the investigator if pregnancy is discovered either during or within 6 months of completing treatment with lucitanib. This also applies to male patients whose

partners become pregnant while the patient is on study, or within the 6-month period after the last dose of lucitanib.

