7.2 Method of Assigning Patients to Treatment Groups

After confirming that patients fulfill entry criteria, the Investigator or his/her delegate will enroll patients as follows:

- Cohorts A and C (non-PK sub study patients): enrollment in IWRS on C1D1 to receive lucitanib at 10 mg daily*
- PK sub study patients: manual enrollment at Day -7 visit to receive single dose of 10 mg lucitanib in a tablet formulation, followed by enrollment in IWRS on C1D1 to receive lucitanib at 10 mg daily*

Based on analysis of data from the PK sub study and confirmation of acceptable PK comparability, patients may begin lucitanib treatment with the tablet formulation upon enrollment and patients who began treatment with capsule formulation may, at the discretion of the Sponsor and Investigator, be switched to the tablet formulation.

*Treatment should be initiated within 3 days of enrollment.

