^C Procedures required prior to lucitanib administration on C1D1 may be omitted if completed ≤ 3 days earlier during the screening period. The total time from the Day -7 visit to the Cycle 1 Day 1 visit must not be fewer than 7 days, but may be greater than 7 days, if necessary.

^D Vital signs (BP, pulse, and temperature) taken pre-dose on drug administration days and post-dose following collection of the 24 hr PK samples on Day -7 and Day 1; height is only required once at screening. BP self-monitoring, two times per week, is requested from patients, including between Day -7 and Day 1 (see [Section 9.5.1.3](#)).

^E Patients are to continue using effective contraception for 6 months after the last dose of lucitanib and report any pregnancies during this period.

^F Serum β -hCG (evaluated by local labs) will be performed only on women of childbearing potential ≤ 7 days prior to C1D1 and End-of-Study. If the serum pregnancy test results are not available on Day 1, a urine pregnancy test can be performed on Day 1 to confirm that the patient is not pregnant prior to dosing.

^G Includes hemoglobin, hematocrit, WBC and differential (with ANC), platelet count, PT/PTT, and reticulocyte count ≤ 14 days prior to the first day of dosing. Blood will be sent for analysis at a local laboratory and must be reviewed by the investigator prior to start of lucitanib administration. Additional tests may be performed at the investigator's discretion.

^H Includes TSH, T3, T4, total protein, albumin, creatinine, BUN or urea, total bilirubin, alkaline phosphatase, ALT, AST, glucose, sodium, magnesium, potassium, chloride, CO₂, calcium, and phosphorus ≤ 21 days prior to first day of dosing. Total cholesterol will be completed during screening only. Blood will be sent for analysis at a local laboratory and must be reviewed by the investigator prior to start of lucitanib administration.

^I Includes dipstick for protein, glucose, blood, pH, and ketones. If dipstick findings are abnormal, then a microscopic evaluation will be performed to assess the abnormal findings.

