9.1 Screening Period

Following written informed consent, and unless otherwise specified, the following assessments should be performed during the 28-day period prior to the first dose of lucitanib. Assessments performed prior to patient signing informed consent are acceptable only if confirmed to have been standard of care.

Up to 20 patients enrolled in Cohort A and Cohort C will participate in a PK sub study at select sites. These patients should have all screening assessments performed within the 21-day period prior to the first dose of lucitanib, i.e., between Day –28 and Day –8 (Table 5).

- Medical history, including demographic information (birth date, race, gender, etc.), smoking status, and oncology history including date of cancer diagnosis, prior cancer treatment, and any surgical procedures
- Documentation of tumor tissue results demonstrating *FGFR1* or 11q amplification (Cohorts A and B) or *FGFR1* and 11q non-amplification (Cohort C) by established laboratory methods (e.g., FISH, NGS, CGH, CISH, or qPCR); or local assessment in blood using validated methods for detecting CTCs or ctDNA
 - For patients without local test results of *FGFR1* or 11q amplification, or *FGFR1* and 11q non-amplification, a separate prescreening consent will be available to enable testing before initiating additional CO-3810-025 specific screening. Patients must read and sign a separate prescreening consent form to undergo testing of tissue by the central laboratory. Upon central confirmation of *FGFR1* or 11q amplification, or *FGFR1* and 11q non-amplification, patients may consent for and begin screening for the study.
- Complete physical examination by body system, height, and weight
- ECOG performance status
- Vital signs (BP, pulse, and temperature)
- Prior and concomitant medications and procedures
- Contraceptive counseling
- Serum pregnancy test (by local laboratory) ≤ 7 days prior to the first day of dosing for women of childbearing potential. If the serum pregnancy test results are not available prior to dosing, a urine pregnancy test can be performed to confirm that the patient is not pregnant prior to dosing. Both values should be entered in the eCRF
- Hematology (hemoglobin, hematocrit, white blood cell [WBC] and differential [with ANC], platelet count, PT/partial thromboplastin time (PTT), and reticulocyte count) ≤ 14 days prior to the first day of dosing

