9.5.1.2 Clinical Laboratory Investigations

Certified local laboratories will perform study-related clinical laboratory tests according to institutional procedures, and the results will be reviewed by the investigator. The panels of laboratory tests to be performed are shown below:

Hematology: Hemoglobin, hematocrit, WBC and differential (with ANC), platelet count, PT/PTT, and reticulocyte count per the schedule of evaluation at screening, during treatment, and at the end-of-study visit. Hematology results must be reviewed by the investigator prior to the start of treatment with lucitanib.

Clinical Chemistry: TSH, T3, T4, total protein, albumin, creatinine, BUN or urea, total bilirubin, alkaline phosphatase, ALT, AST, glucose, sodium, potassium, chloride, CO₂, calcium, magnesium, and phosphorus per the schedule of evaluations at screening, during treatment, and at the end-of-study visit. Total cholesterol will be performed at screening only.

Urinalysis: Performed on freshly voided clean sample by dipstick for protein, glucose, blood, pH, and ketones per the schedule of evaluations. If dipstick findings are abnormal, then a microscopic evaluation will be performed to assess the abnormal findings. Urinalysis will be performed at screening, during treatment, and at the end-of-study visit.

Serum Human Chorionic Gonadotropin β (β -hCG) Pregnancy Test: Performed on women of childbearing potential ≤ 7 days prior to administration of the first dose of lucitanib, and at the end-of-study visit. If the serum pregnancy test results are not available prior to the first dose of lucitanib, a urine pregnancy test can be performed to confirm that the patient is not pregnant prior to dosing. Both values should be entered in the eCRF. A negative result must be confirmed by a physician before the first dose of lucitanib can be administered.

Laboratory reports will be reviewed by the investigator or delegated physician to assess clinical significance. Clinically significant abnormalities should be documented in the eCRF as an AE as defined in [Section 10.4](#).

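### In the PK sub-study, Table 5 footnote F times the pregnancy test from C1D1 rather than from the Day -7 first dose, so its window opens on or after first exposure

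*Protocol*

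**What the plan says.** Table 5 in Section 9 is the schedule for PK sub-study patients only.

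- **Footnote F, serum test:** at most 7 "days prior to C1D1 and End-of-Study", in women of childbearing potential.
- **Footnote F, fallback:** when the serum result has not come back by Day 1, the footnote says that "a urine pregnancy test can be performed on Day 1 to confirm that the patient is not pregnant prior to dosing".
- **Table 5 grid:** the test is marked only in the screening column (Day -28 to Day -8) and at End-of-Study.
- **Footnote C:** the time from the Day -7 visit to C1D1 "must not be fewer than 7 days, but may be greater than 7 days, if necessary".
- **First dose:** under Section 7.2, sub-study patients are enrolled at the Day -7 "visit to receive single dose of 10 mg lucitanib in a tablet formulation". Section 5.1.1 also treats Day -7 as the first dose when it sets the sub-study screening period.

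The body of the protocol counts from the first dose throughout:

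- **Section 6.2, criterion 11:** "a negative pregnancy test within 7 days prior to initiation of the study drug".
- **Section 6.4:** "negative serum pregnancy less than 7 days prior to administration of the first dose lucitanib".
- **Section 9.1:** at most 7 "days prior to the first day of dosing for women of childbearing potential".
- **Section 9.5.1.2:** the same 7-day limit before the first dose, and "A negative result must be confirmed by a physician before the first dose of lucitanib can be administered".

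**The concern.** In Table 4, which covers everyone outside the sub-study, C1D1 is the first dose, so the same footnote wording is correct there. In Table 5 the first dose comes at least a week before C1D1, yet the wording was kept. A window meant to fall before exposure then falls on or after it, and the urine test meant to clear the patient for dosing comes after she has already been dosed.

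The test exists to stop a pregnant woman from being exposed. Section 3.5.3 reports that lucitanib was genotoxic and clastogenic in all three genotoxicity studies conducted, and Section 6.4 discourages hormonal contraceptives. Sub-study participation is required of Cohort C patients until the sub-study is full (Section 5.1). A pregnancy first detected by the Day 1 fallback would be detected after a full single dose.

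**Working it through.** This is day counting; no sample size or error rate is involved.

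**Convention.** There is no Day 0. This is implied by the 7-day minimum from Day -7 to Day 1 (footnote C) and by Section 9.1, where the 21 days before the first dose are Day -28 to Day -8. A Day 0 would only lengthen the distance to C1D1.

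**Set-up.** Put C1D1 at 0 and the first dose at -g, where g is the gap in days and g ≥ 7.

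- Footnote F window: -7 to 0 (8 calendar days).
- First-dose rule (criterion 11, Sections 9.1 and 9.5.1.2): -g-7 to -g.
- Table 5 screening column: -g-21 to -g-1.

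**Step 1: where the footnote window falls.** It opens g - 7 days after the first dose. The gaps above 7 are examples, since footnote C states no maximum.

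| Gap g | Window opens, days after first dose | Window days strictly after first dose | Days shared with first-dose rule | Days shared with screening column |
|---|---|---|---|---|
| 7 | 0 | 7 of 8 | 1 (Day -7 itself) | 0 |
| 8 | 1 | 8 of 8 | 0 | 0 |
| 10 | 3 | 8 of 8 | 0 | 0 |
| 14 | 7 | 8 of 8 | 0 | 0 |

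**Step 2: can a screening test meet footnote F?** Distance from C1D1 = age of the test at the Day -7 dose + g. The smallest value is 1 + 7 = 8 days, which exceeds 7. So 0 of the 21 screening days qualify, whatever the gap.

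**Step 3: which screening days meet the first-dose rule?** A Day -28 test is 21 days old at the Day -7 dose; a Day -8 test is 1 day old. An age of 7 days or less gives Day -14 to Day -8, which is 7 of 21 days; the other 14 fail. Section 6.4 says less than 7 days, which gives Day -13 to Day -8, or 6 of 21.

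**Step 4: the urine fallback.** Day 1 is g days after the first dose, so at least 7 days after exposure.

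**Step 5: does another list repair this?** No. Neither the Day -7 list (Section 9.2.1) nor the sub-study C1D1 list (Section 9.2.2) contains a pregnancy test. The ±2-day tolerance in footnote B applies only where no other window is specified, and footnote F specifies one.

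**Step 6: carry-over or intended second test?** Footnote F has the same wording in Tables 4 and 5. Other Table 5 footnotes suit the sub-study: G and H count from the first day of dosing, and H was shortened from 28 days in Table 4 to 21. Had a second test near C1D1 been intended, the grid would show a mark at Day -7 or Day 1, and it shows none. Carry-over is the more likely explanation.

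**The case against.** The strongest reply is that the safeguard already exists in binding text. Criterion 11 requires the test before study drug, Section 6.5 allows no waivers, Sections 7.2 and 9.2 require eligibility to be confirmed before enrolment, and Section 9.5.1.2 requires physician confirmation of a negative result. Sections 6.4, 9.1 and 9.5.1.2 already provide a urine fallback before dosing. This stands, and it limits the harm: the defect is a conflicting schedule, not a missing safeguard. It does not make the footnote right, because a site that times the test by footnote F tests at the wrong time.

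A second reply is that the 21-day age and the 14 failing days come from reading the screening column alone. A general screening column is normally narrowed by specific rules, and Table 4 also places a 7-day test inside a 28-day screening period. This is fair. The results specific to the defect are the 0 of 21 days that meet footnote F and the opening of its window on or after first exposure. In Table 5, however, the footnote that should narrow the column points to the wrong date.

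Third, a test taken before dosing on Day -7 meets both rules. That holds only at a gap of exactly 7 days, and nothing schedules a test then.

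Fourth, moving the anchor removes the only text calling for a test near the start of daily dosing. At a 14-day gap, a Day -14 test would be 7 + 14 = 21 days old at C1D1. But neither the Table 5 grid nor Section 9.2.2 schedules a test there, so no planned test is lost.

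**Conclusion.** The concern holds. Footnote F of Table 5 is wrong as written: its window starts on the day of the first dose at best, no day in the table's own screening column can meet it, and its fallback comes at least 7 days after exposure. It contradicts four other places in the protocol.

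The consequence is bounded. Untested dosing is unlikely given the eligibility rules, and no endpoint, population or analysis in the SAP is touched. At most, the issue reaches women of childbearing potential among up to 20 patients, or more if the sub-study is enlarged as Section 6.1 permits; the documents do not give their number. It should be corrected because the instruction concerns fetal exposure to a genotoxic drug and gives the wrong timing if followed.

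The conclusion rests on Day -7 being the first dose, which Sections 5.1.1 and 7.2 and Table 5 footnote M all support, and on the 7-day minimum gap. The day counts use the no-Day-0 convention.

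**What to change.** In Table 5 footnote F:

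- Replace C1D1 with the first dose of lucitanib (Day -7). The End-of-Study test stays.
- In the fallback sentence, change Day 1 to Day -7 in both places, so that the urine test is done on Day -7 before the tablet is given when the serum result is not yet available.

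Leave Table 4 footnote F as it is. Day -14 to Day -8 then become the qualifying screening days, in agreement with criterion 11 and Sections 9.1 and 9.5.1.2. Section 6.4 remains one day stricter (Day -13 to Day -8), and its limit could be aligned in the same amendment.

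The cost is two date anchors in one footnote, with no added visit or serum test.

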9.1 Screening Period

Following written informed consent, and unless otherwise specified, the following assessments should be performed during the 28-day period prior to the first dose of lucitanib. Assessments performed prior to patient signing informed consent are acceptable only if confirmed to have been standard of care.

Up to 20 patients enrolled in Cohort A and Cohort C will participate in a PK sub study at select sites. These patients should have all screening assessments performed within the 21-day period prior to the first dose of lucitanib, i.e., between Day –28 and Day –8 (Table 5).

- Medical history, including demographic information (birth date, race, gender, etc.), smoking status, and oncology history including date of cancer diagnosis, prior cancer treatment, and any surgical procedures
- Documentation of tumor tissue results demonstrating *FGFR1* or 11q amplification (Cohorts A and B) or *FGFR1* and 11q non-amplification (Cohort C) by established laboratory methods (e.g., FISH, NGS, CGH, CISH, or qPCR); or local assessment in blood using validated methods for detecting CTCs or ctDNA
 - For patients without local test results of *FGFR1* or 11q amplification, or *FGFR1* and 11q non-amplification, a separate prescreening consent will be available to enable testing before initiating additional CO-3810-025 specific screening. Patients must read and sign a separate prescreening consent form to undergo testing of tissue by the central laboratory. Upon central confirmation of *FGFR1* or 11q amplification, or *FGFR1* and 11q non-amplification, patients may consent for and begin screening for the study.
- Complete physical examination by body system, height, and weight
- ECOG performance status
- Vital signs (BP, pulse, and temperature)
- Prior and concomitant medications and procedures
- Contraceptive counseling
- Serum pregnancy test (by local laboratory) ≤ 7 days prior to the first day of dosing for women of childbearing potential. If the serum pregnancy test results are not available prior to dosing, a urine pregnancy test can be performed to confirm that the patient is not pregnant prior to dosing. Both values should be entered in the eCRF
- Hematology (hemoglobin, hematocrit, white blood cell [WBC] and differential [with ANC], platelet count, PT/partial thromboplastin time (PTT), and reticulocyte count) ≤ 14 days prior to the first day of dosing
- Serum chemistry (TSH, T3, T4, total protein, albumin, creatinine, blood urea nitrogen [BUN] or urea, total bilirubin, alkaline phosphatase, ALT, AST, glucose, sodium, potassium, chloride, CO₂, calcium, magnesium, phosphorus, and total cholesterol)

- Urinalysis performed on freshly voided clean sample (dipstick for protein, glucose, blood, pH, and ketones). If dipstick findings are abnormal based on investigator judgment, then a microscopic evaluation will be performed to assess the abnormal findings
- Tumor assessments. Assessments should consist of clinical examination and computed tomography (CT) scans of the chest, abdomen, and pelvis with intravenous contrast and appropriate slice thickness per RECIST Version 1.1; other alternative studies (magnetic resonance imaging [MRI] and X-ray) may be performed if clinically indicated. The same methods used to detect lesions at baseline are to be used to follow the same lesions throughout the clinical study
- Brain imaging is required at baseline. Patients with brain lesions detected at baseline require repeat brain imaging as part of the follow-up tumor assessments. The same methods used to detect brain lesions at baseline are to be used to follow the same lesions throughout the clinical study
- Archival FFPE tumor specimen for central laboratory confirmation of *FGFR1* or 11q amplification status and companion diagnostic development is required. Detailed sample handling instructions are provided in the Laboratory Manual
- Blood sampling for ctDNA analysis. Detailed sample handling instructions are provided in the Laboratory Manual
- Blood sampling for biomarker analysis. Detailed sample handling instructions are provided in the Laboratory Manual
- 12-lead ECG (in triplicate, 10-sec tracings >2 min apart)
- LVEF (ECHO or MUGA)

At the end of screening, patients may be enrolled to receive daily treatment with lucitanib 10 mg (see [Section 7.2](#)).

9.2 Treatment Period

Before enrolling a patient, all eligibility criteria must be satisfied.

Patients will receive lucitanib 10 mg daily. Beginning on Day 1, lucitanib will be administered once daily to be swallowed with water (240 mL or 8 ounces). Patients should take lucitanib at approximately the same time each day, on an empty stomach, at least 2 hours before and 2 hours after a meal. Patients will record the dose and timing of administration of oral lucitanib in their daily dosing diary. Treatment with lucitanib is continuous but cycles will be defined as 28 days in duration.

BP self-monitoring should be completed at least twice a week by patients and measurements should be recorded in their diaries and brought to the clinic visits for review (see [Section 9.5.1.3](#)).

Unless otherwise specified, all patients will undergo the following procedures and assessments.

9.2.1 Day -7 PK Sub Study

The following pre-dose and post-dose assessments will be performed at Day -7 for patients participating in the PK sub study:

Pre-dose Assessments	Post-dose Assessments

 • Complete physical examination • Weight • ECOG performance status • Vital signs (BP, pulse, and temperature) • Concomitant medications • Hematology (including reticulocyte count) and serum chemistry • Urinalysis • AE monitoring • 12-lead ECG (in triplicate, 10-sec tracings >2 min apart) 5–10 min prior to dosing • PK blood sample (5–10 min prior to dosing) 	
 • 12-lead ECG (in triplicate, 10-sec tracings >2 min apart), 2 hours (± 5 min) following dosing with lucitanib • AEs experienced by the patient since dosing will be documented • Concomitant medications administered since dosing will be recorded • PK blood sampling collected at the following time points: 15 (± 2) min, 30 (± 3) min, 1 hr (± 5 min), 1.5 hr (± 5 min), 2.5 hr (± 10 min), 4 hr (± 15 min), 6 hr (± 15 min), 8 hr (± 15 min), 10 hr (± 30 min) (optional), and 24 hr (± 30 min) • Vital signs (BP, pulse, and temperature) taken after last PK sample

